Would it be possible for your child to and get sweet snacks on their own, without your help?	 Yes  No
If we visited your home today, how many different sweet snacks do you have in your home?	
Would it be possible for your child to get soda on their own, without your help?	 Yes  No
Over the last month, how often did you eat lettuce salad (with or without other vegetables)?	
Each time you ate lettuce salad, how much did you usually eat?	
Over the last month, how often did you eat French fries or fried potatoes?	
Each time you ate French fries or fried potatoes, how much did you usually eat?	
Over the last month, how often did you eat other white potatoes?	
Count baked, boiled, and mashed potatoes, potato salad, and white potatoes that were not fried.	
Each time you ate these potatoes, how much did you usually eat?	
Over the last month, how often did you eat cooked dried beans?	
Count baked beans, bean soup, refried beans, pork and beans and other bean dishes.	
Each time you ate these beans, how much did you usually eat?	
Think about all the foods you ate at your morning meal and morning snacks this past week. On how many days did you eat vegetables for your morning meal or morning snacks?	
When your child ate vegetables with breakfast, what is the total amount of vegetables they usually ate?	

When your child ate vegetables with breakfast, what is the total amount of vegetables they usually ate?	
Think about all the foods you ate at your lunch meal and lunch snacks in the past week. On how many days did you eat vegetables for your lunch meal?	
When your child ate vegetables with lunch, what is the total amount of vegetables they usually ate?	
Think about all the foods you ate at your dinner/supper meal and snacks in the past week. On how many days did you eat vegetables for your dinner meal?	
When your child ate vegetables with dinner, what is the total amount of vegetables they usually ate?	

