Think about all the foods your child ate for snacks in the past week. How often did they eat vegetables as snacks?	
When your child ate vegetables as snacks, what is the total amount of vegetables they usually ate?	
Over the last month, how often did you eat mixtures that included vegetables?	
Count such foods as sandwiches, casseroles, stews, stir-fry, omelets, and tacos.	
Over the last month, how often did your child eat tomato sauce? Include tomato sauce on pasta or macaroni, rice, pizza and other dishes.	
Over the last week, how often did your child eat tomato sauce?	
(Include tomato sauce on pasta or macaroni, rice, pizza and other dishes)	
Over the last week, how often did you eat vegetable soups?	
Include tomato soup, gazpacho, chicken soup with vegetables	
When your child ate vegetable soup, how much did they usually eat?	
Where do you eat dinner?	 In the same place every night (example - a dining room or kitchen)  A different place most nights  Almost every week night  2-4 times per week  0-1 times per week nights
I eat dinner with my children....	

Do you have the following at home?	 Microwave  Blender  Measuring cups AND spoons  A pot  Frying Pan
How do you usually heat your food?	 Oven / Stove  Microwave  Hot Plate  I do not have a place to heat food  Other
Would you say that you have adequate space to prepare food in your kitchen?	 Yes  No 
reset

Do you share a cooking space with individuals who are not in your family?	 Yes  No 
reset

Do you and your children eat dinner together (all in one room at the same time) or apart (different rooms or different times)?	
What do you drink with your dinner?	

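### In the example survey, four of nine food frequency/amount pairs ask how often the guardian ate but how much the child ate, and the 60-minute activity item mixes the two; separately, knowledge is hypothesized but never measured

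*Combined protocol and SAP*

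**What the plan says.** Section 3.4 takes the primary outcomes from a telephone survey of the guardian covering food frequency, screen time, physical activity, and self-efficacy and confidence. It presents Appendix C as an example, allows questions to be changed or dropped after feedback from the advisory board or the community health workers, and requires IRB approval of the final version before data collection.

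Four food items in Appendix C pair a frequency question with an amount question about a different person:

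- Breakfast: "On how many days did you eat vegetables for your morning meal or morning snacks", then "When your child ate vegetables with breakfast, what is the total amount of vegetables they usually ate".
- Lunch: "On how many days did you eat vegetables for your lunch meal", then "When your child ate vegetables with lunch, what is the total amount of vegetables they usually ate".
- Dinner: "On how many days did you eat vegetables for your dinner meal", then "When your child ate vegetables with dinner, what is the total amount of vegetables they usually ate".
- Vegetable soup: "Over the last week, how often did you eat vegetable soups", then "When your child ate vegetable soup, how much did they usually eat".

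One activity item asks on how many of the past seven days the guardian was active for 60 minutes, then instructs the respondent to total the child's active time. The next item counts how many times the child was active. The one after that asks how long the child is active on one of the days in question.

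Knowledge appears with self-efficacy and behaviors in the objective (Abstract and Section 1.1) and in the research question, null and alternative hypotheses (Section 1.2). It is not among the primary or secondary outcomes in Section 3.4, nor among the analysis variables in the Abstract or Section 4.2.

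**The concern.** A weekly amount needs the number of eating days and the usual amount per day for the same person. For the four mixed items the child has an amount but no matching frequency, and the guardian has a frequency but no matching amount. Section 3.1 makes higher vegetable consumption an aim of the program, and diet is a primary outcome, so the main meals are where one would most want an intake figure.

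The 60-minute item can be answered for either person. Two guardians, or one guardian in two survey rounds, could report on different people without the data showing it.

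The knowledge gap is a separate matter and does not depend on the survey wording: one of the three constructs in the hypothesis has no outcome and no analysis.

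**Working it through.** There is no plan figure to reproduce. The check is a count of items in Appendix C, coding each question by the person it asks about. Lines repeated at a page break are counted once.

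| Food item | Frequency is about | Amount is about | Same person |
|---|---|---|---|
| Lettuce salad | guardian | guardian | yes |
| French fries | guardian | guardian | yes |
| Other white potatoes | guardian | guardian | yes |
| Cooked dried beans | guardian | guardian | yes |
| Breakfast | guardian | child | no |
| Lunch | guardian | child | no |
| Dinner | guardian | child | no |
| Snacks | child | child | yes |
| Vegetable soup | guardian | child | no |

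- **Pairs:** 4 guardian only + 1 child only + 4 mixed = 9. Mixed share: 4/9 = 44%. Vegetable mixtures and tomato sauce have frequency questions but no amount question, so they are not pairs.
- **Eating occasions** (breakfast, lunch, dinner, snacks): a vegetable amount per week can be formed for the child in 1 of 4 (snacks) and for the guardian in 0 of 4. For soup it can be formed for neither.
- **What survives:** each guardian frequency and each child amount as a single item. Earlier in Appendix C, the child's overall vegetable frequency over the past seven days is asked with no change of subject. That item is not matched to a meal or to soup, so it does not restore the missing amounts.
- **Activity items:** 2 about the guardian (activity in the past month; being active in the child's presence), 1 that changes subject (60 minutes), and 4 about the child (times active, duration, moderate-activity days, walking days), total 7. One of the 7 is ambiguous. One, the duration item, is loosely worded: it refers back to days, but the item before it counts times, and the nearest earlier day count is the ambiguous 60-minute item. The other 5 have neither fault.
- **Knowledge:** 0 outcomes in Section 3.4 and 0 analysis variables in the Abstract or Section 4.2. In the survey text available, which ends at a screen-time question, there are 0 knowledge items. The closing questions ask about confidence or a perceived need to change, which are different constructs.

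**The case against.** The strongest reply is that this is a draft. Section 3.4 says so, and the final version must pass the IRB. That stands, and it limits the point to the version shown. But nothing in Section 3.4 commits anyone to checking that paired questions concern the same person, and the time before submission is the cheapest time to do it.

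A second reply is that the guardian will understand the child to be meant, or will ask. The script does invite requests for clarification, but it does not tell the interviewer which person is intended. The same block uses the second person for the guardian in four consistent pairs and names the child in the snack pair. Answer lists are not visible, so a label that settles the person cannot be ruled out.

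A third reply is that guardian meal frequency is worth having, since the research question concerns guardians' behavior. That is right. Only the combination of frequency and amount fails.

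A reader might infer more than the documents support:

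- *That the primary diet or activity outcome is invalid.* Section 4.2 does not say which items are scored, so this is not shown.
- *That the items are useless.* They can be reported singly.
- *That a distortion can be sized.* With assumed values, 5 guardian days standing in for 2 to 7 child days would give 5/2 = 2.5 to 5/7 = 0.71 times the child's true weekly amount. No section prescribes that product, so the range warns against forming it and does not measure error in the trial.
- *That one group is favored.* The wording is the same in both.
- *That Section 5.2 is wrong to list improved knowledge as a benefit.* An expected benefit of education need not be a measured outcome.

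**Conclusion.** The point holds within limits. Used as written, the example survey yields no weekly vegetable amount at main meals or from soup for guardian or child (4 of 9 pairs), and the subject of one of seven activity items is ambiguous. The loose duration item is minor. These counts are certain for the text shown. Their consequence depends on the final instrument, the Spanish version, the answer lists and the scoring rule, none of which is in the documents.

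The knowledge gap is firmer because it rests on the protocol's own outcome and analysis sections: that part of the hypothesis cannot be tested as planned. The absence of knowledge items can be confirmed only for the survey text available.

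This should be corrected, because the faults are plain and the repair is cheap, but nothing here shows the study's comparison to be unsound.

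**What to change.** Before the final survey goes to the IRB:

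- Make each of the four mixed pairs, and the 60-minute item, refer to one person throughout. If the child is the target, the snack pair is the model.
- Tie the duration item to a stated count of days.
- Check the Spanish version for the same faults.
- Score child and guardian items separately, and name in Section 4.2 the items that form each score.

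If the survey is already in use, do not multiply frequency by amount for the mixed pairs. Report the guardian's frequency and the child's amount as separate items.

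For knowledge, either add a few questions and list it in Sections 3.4 and 4.2, or take it out of the objectives, research question and hypotheses. Section 5.2 can stay as it is.

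Cost: six reworded items (four frequency questions, the 60-minute item and the duration item). They fit within the IRB submission that Section 3.4 already requires, or need a small amendment if the survey is in use. Changing the knowledge text amends an approved protocol. If knowledge questions are added, an assumed 1 to 2 minutes on a call of about 15 minutes is 1/15 = 7% to 2/15 = 13% longer. For 50 families that is 50 × 2 × 1 to 2 = 100 to 200 interviewer minutes over the two surveys in Section 3.4, or 50 × 3 × 1 to 2 = 150 to 300 over the three time points in Section 4.2.

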1. INTRODUCTION

1.1. Specific Aims

Obesity rates are significantly higher among Hispanic youth in the United States, disproportionately putting these children at an increased risk for obesity-related diseases such as hypertension, dyslipidemia, and impaired glucose tolerance. Despite this disparity, there is a lack of literature pertaining to culturally relevant and family-centered interventions for Hispanic youth and their families. While virtual programming offers an innovative option for pediatric weight management, limited data exists on the efficacy of telehealth /virtual interventions for this population and their guardians.

The purpose of this community-engaged quasi-experimental study is to determine whether a family-based, culturally tailored, virtual intervention enables guardians to shape the weight-related aspects of their home environments and the lifestyle behavioral practices (diet, exercise, screen behaviors) to be more supportive of their family's optimal health and weight, compared to standard in-office counseling alone. Specifically, the study intends to compare the effectiveness of an expanded virtual educational program (x-IHPC) at modifying knowledge, self-efficacy, and behaviors when compared to traditional in-office counseling for guardians of children who are obese or overweight.

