1.2. Hypothesis

Research Question: Among guardians of children ages 6-12 years who are obese or overweight, does a family-based, culturally-tailored, virtual intervention change knowledge, self-efficacy, and behaviors about modifiable lifestyle practices to promote healthy eating when compared to standard in-office counseling?

Ho: A family-based, culturally-tailored, virtual intervention does not significantly change knowledge, self-efficacy, and behaviors about modifiable lifestyle practices when compared to standard in-office counseling.

Ha: A family-based, culturally-tailored, virtual intervention does significantly change knowledge, self-efficacy, and behaviors about modifiable lifestyle practices when compared to standard in-office counseling.

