The x-IHPC will include 4 extra modules, (= 4 additional weeks of programming) that will be developed by a dietitian curriculum specialist. The expanded IHPC will also include programming just for parents to increase their involvement. A key pillar of this study is identifying and training CHWs from HWNV to be Spanish-language facilitators of x-IHPC. Training these CHWs and including them in designing the x-IHPC curriculum will ensure that the programming is culturally appropriate; includes local features that relate directly to the community's needs; and enables facilitators to respond effectively to the questions and learning needs of the parents and children involved in the program.

IHPC provides produce boxes, nutrition and meal-preparation, education, and supportive counseling to address barriers related to obtaining produce and food. The intervention provides participants with a bi-weekly produce box for 12 weeks (6 boxes total) and helps families identify sustainable ways to obtain vegetables once the produce boxes end. Providing produce boxes exposes families to new, unfamiliar vegetables that are not common in their home countries, and allows families to experiment with new recipes on a limited income. The CHW will support families by coaching them on how to prepare these unfamiliar vegetables, give tips on finding sales at grocery stores, as well as by navigation to food assistance sites including food pantries, school meal sites and bus routes, and neighborhood food distributions. Parents will learn strategies to increase vegetable consumption by addressing perceived

barriers – such as the child doesn't like vegetables. Curriculum will also include topics such as how to increase physical activity and reduce screen time. Both the families in the x-HPC and families who receive the in-office counseling will be offered the 6 vegetable food boxes, delivered on a bi-weekly basis during their time in the study.

Families will decide if they have the capacity to participate in the x-HPC intervention. They will be offered both groups, but can choose which group works for their family. We realize that this introduces selection bias into the study (families who self select to be part of the intervention are families who are interested in health and have the time and ability to attend). However, the intervention takes a lot of time and families need to choose the arm that works for their schedule.

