3.4. Endpoints/Outcomes Measurements

3.4.1. Primary outcomes.

3.4.2.

Primary outcomes measured via a survey, which will include food frequency questionnaires, screen time estimates, physical activity questionnaires, estimated screen time reports, and guardian self-efficacy and confidence questions related to modifiable lifestyle behaviors.^{15 16 17} Survey data will be collected during phone calls from the PI or CHW at the outset of the study and then again at the conclusion of the study. An example survey has been included (Appendix C: Survey). The survey questions may be altered or deleted based on feedback from the study advisory board or the CHWs, as this study is based on community engagement and feedback. The final survey instrument will be submitted to this IRB for approval before the data collection begins.

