4.2. Method of Data Analysis

Analyses will follow the intention-to-treat principle, which categorizes participants by their treatment assignments regardless of adherence to the intervention or incomplete follow-up, and includes them in all analyses. Descriptive statistics will be calculated and reported as mean, standard deviation and 95% confidence intervals for continuous variables and frequency and percentage for categorical variables. Characteristics of study participants will be compared at baseline between the intervention and control groups and tested for significance using the two-sample t-test for continuous variables and the Chi-square test for categorical variables. Comparisons that are significant at the $P<0.10$ level will be considered for inclusion in multivariable models for primary and secondary analyses given that participants will not be randomized to their respective treatment groups.

Primary analyses will examine diet quality, screen time, physical activity, and guardian self-efficacy and confidence of those in the intervention and control groups while controlling for the correlated nature of the repeated measures within participants (i.e. baseline, post-intervention, and 6-month post-intervention). Secondary analyses will compare the BMI of guardians and BMI percentile of children at the three time points between the intervention and control groups. A longitudinal data analysis strategy will be employed with generalized estimating equations with robust CIs for both primary and secondary outcomes (Albert, 1999; Ma et al., 2012). A 2-sided p-value <0.05 will be accepted to indicate statistical significance. Additional analyses will be conducted to determine if results were influenced by other covariates including demographics (age, gender, educational attainment of guardian, income, etc.). All analyses will be conducted in SAS version 9.2.

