During the last 7 days, on how many days did < child> walk for at least 10 minutes at a time?	
How much water does your child drink each day?	
Do you feel that you need to change the amount of fruits and vegetables your child eats each week?	
How confident do you feel that you can increase the number of vegetables your child eats each week?	
How confident do you feel that you can obtain fresh fruit and vegetables for your family to eat during the week?	
How confident do you feel that you can cook healthy meals for your family?	
Do you feel that you need to change the amount of time your child spends using screens?	

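### All three guardian confidence questions visible in the example survey are about food, while the primary self-efficacy outcome is worded for lifestyle behaviors in general

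*Combined protocol and SAP*

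**What the plan says.** Section 3.4 includes among the primary outcomes "guardian self-efficacy and confidence questions related to modifiable lifestyle behaviors". Section 4.2 carries this into the analysis: "Primary analyses will examine diet quality, screen time, physical activity, and guardian self-efficacy and confidence". The alternative hypothesis in section 1.2 is that the intervention "does significantly change knowledge, self-efficacy, and behaviors about modifiable lifestyle practices when compared to standard in-office counseling"; it is not limited to food. Section 1.1 names the target as "lifestyle behavioral practices (diet, exercise, screen behaviors", that is, three areas. The intervention is meant to reach all three: section 3.1 says, "Curriculum will also include topics such as how to increase physical activity and reduce screen time".

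Appendix C gives the survey. Its visible confidence questions are "How confident do you feel that you can increase the number of vegetables your child eats each week", a second on obtaining fresh fruit and vegetables for the family, and "How confident do you feel that you can cook healthy meals for your family". The last visible question is "Do you feel that you need to change the amount of time your child spends using screens".

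Section 3.4 presents Appendix C as an example. It allows questions to be changed or removed after comment from the advisory board and the community health workers, and it sends the final version to the IRB before data collection.

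**The concern.** The outcome has a wide name and, on the visible items, a narrow measure. If the survey were used as shown, a rise in guardians' confidence about vegetables and cooking would be reported as a rise in self-efficacy about lifestyle behaviors. A rise in confidence about screens or activity, both of which the curriculum teaches, would have no question to register it. A reader of the results would take a food finding as evidence for the lifestyle-wide hypothesis, or take a null food finding as evidence against it.

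The wording of the scope is also uneven within section 1.2. The research question ties the lifestyle practices to healthy eating, while the null and alternative hypotheses just below it do not.

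**Working it through.** The plan gives no figure for this point, so the check is a count by reading. I took every question in Appendix C that asks how confident the guardian feels, classified it by area, and set the result beside the three areas in section 1.1.

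| Area (section 1.1) | In the x-IHPC curriculum (section 3.1) | Behavior questions visible | Need-to-change questions visible | Confidence questions visible |
|---|---|---|---|---|
| Diet | yes | yes | 1 | 3 |
| Physical activity | yes | yes | 0 | 0 |
| Screens | yes | yes | 1 | 0 |
| Total | | | 2 | 3 |

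Food therefore accounts for 3 of 3 confidence questions, and 1 of 3 areas has any.

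*Could another question fill the gap?*

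- The behavior questions cannot. Appendix C asks about hours of TV and of games or computer use, how often the guardian restricts computer time, how often and how long the child is active, and days of walking. These record what happens at home, not how able the guardian feels to change it. Section 4.2 makes the same distinction by listing screen time and physical activity apart from self-efficacy and confidence.
- The screen question quoted above cannot either. It asks whether the guardian sees a need to change. A guardian may see the need and feel unable to act, or feel able and see no need.
- For physical activity there is neither a confidence question nor a need-to-change question in the visible text.

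*Does the visible text settle what the final survey contains?* No. The food questions at the end of Appendix C open with a need-to-change item, and the confidence items follow it. The next line is a need-to-change item on screens, and the text stops there. By the same pattern, confidence items on screens could come next, and perhaps a set on activity. The documents neither show nor exclude them.

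**The case against.** The strongest reply is that the gap may lie in the text available here and not in the plan. Appendix C stops at what looks like the opening of a screen block, there is no closing script to match the opening one, and section 3.4 calls the survey an example. Section 3.4 already words the outcome for lifestyle behaviors, so the final instrument may match it. This stands, and it turns the point into a request to confirm, with a remedy if the items are absent. It does not remove the point: section 3.4 lets questions be altered or deleted without requiring that confidence be covered in each area, and neither 3.4 nor 4.2 says which items make up the outcome.

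A second reply is that the research question in section 1.2 refers to healthy eating, which food items fit, and that section 1.1 does not promise a self-efficacy measure in each of its three areas. That also stands in part. It supports the narrower outcome name as an acceptable remedy, but the hypotheses and section 3.4 would then have to be narrowed to agree.

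A reader might go further and infer that the trial can conclude nothing about screen time or physical activity. The documents do not support this. Both are asked about directly and are primary outcomes in their own right in section 4.2. A reader might also infer that the need-to-change items would be pooled with the confidence items and mask or reverse an effect. The plan defines no such score, so that harm cannot be attributed to it.

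**Conclusion.** The point holds in a limited form. On the visible items, guardian confidence is measured in one of three areas while the outcome and hypotheses are worded for all of them. The trial could then support a statement about confidence regarding food and none about confidence regarding screens or activity. The size is a matter of coverage (3 of 3 items on food, 0 on the other two areas); the documents give no basis for expressing it as an effect size.

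This rests on two assumptions: that the final survey has no confidence items beyond those visible, and that the self-efficacy outcome is built from the questions that ask about confidence. If the final survey already covers screens and activity, only the mismatch in scope within section 1.2 and the lack of a stated item list remain.

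**What to change.** Before the final survey goes to the IRB, check that it has one confidence question on limiting the child's screen time and one on increasing the child's physical activity, on the same response scale as the food questions. Add them if they are absent. Name the confidence items in section 3.4, and state in section 4.2 that confidence will be reported by area.

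If the items are not included, restrict the self-efficacy outcome in sections 3.4 and 4.2, and the hypotheses in section 1.2, to confidence about food and healthy eating, which would bring them into line with the research question.

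The first option adds two short questions to a phone interview that the script puts at about 15 minutes, and it uses an IRB submission already planned. The second costs only a few words of text. If baseline calls have already been made without the two items, those families will have no baseline answer on them, and the narrower name is the cleaner choice.
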